### **Zoledronic acid Administration:**

The risks of zoledronic acid therapy are as follows: flu-like symptoms (low-grade fever, fatigue, nausea, muscle aches, joint aches, headache), skin rash, diarrhea, and joint pain. Less common side effects include abdominal or stomach pain; renal impairment and acute renal failure; atrial fibrillation; hypocalcemia; stomach cramping; belching; severe bone, joint, and muscle pain; hypertension; blurred vision or change in vision; chest pain; constipation; cough; dizziness; dry eyes; fever; general feeling of discomfort or illness; leg cramps; nausea; ringing in the ears; swelling of the feet or lower legs; and weakness. On rare occasion, red sore eyes have been reported among those on zoledronic acid therapy.

Two very rare potential complications of bisphosphonate therapy are osteonecrosis of the jaw and atypical femur fractures. Osteonecrosis is a bone condition that results from poor blood supply to an area of bone causing bone death. Although it can affect any bone, only osteonecrosis of the jaw has been found to coincide with bisphosphonate therapy. The vast majority of cases have developed in patients treated with high dose intravenous therapy (94%), and with multiple myeloma or metastatic breast cancer (85%). In the majority of cases of jaw osteonecrosis in the treatment of osteoporosis, dental surgery and/or trauma to the jaw were preceding factors in the development of osteonecrosis of the jaw. The risk of jaw osteonecrosis increases with the length of time one is exposed to intravenous bisphosphonate therapy. The skeleton is constantly developing micro fractures from skeletal loading. These micro fractures are repaired by the normal process of bone remodeling, which requires bone resorption. Bisphosphonates suppress bone remodeling and remain in the skeleton for many years. Long term bisphosphonate use may cause accumulation of micro fractures, thereby increasing skeletal fragility. Atypical subtrochanteric femur fractures are fractures in the bone just below the hip joint. Diaphyseal femur fractures occur in the long part of the thigh bone. These fractures are very uncommon and appear to account for less than 1% of all hip and femur fractures overall. Although it is not clear if bisphosphonates are the cause, these unusual femur fractures have been predominantly reported in patients taking bisphosphonates long term.

Flu-like symptoms can occur in persons receiving intravenously administered bisphosphonates. These flu-like symptoms may include fever, chills, fatigue, headache and nausea, and typically resolve within 2 days. Participants will be advised that they may take over-the-counter acetaminophen 650-1000 mg PO once on the morning of the zoledronic acid infusion as prophylaxis for these symptoms. As bisphosphonates remain in the bones for many years after administration has concluded, it remains unclear as to whether bisphosphonates are released from bone during pregnancy or breastfeeding. Published reports to date have not demonstrated increased birth defects in infants born to women receiving bisphosphonates before or during pregnancy. Study participation by pregnant or breastfeeding women is not allowed and is a study exclusion.

Although the long-term risk of zoledronic acid in young women is unknown, bisphosphonates have been used in premenopausal women to treat osteopenia due to glucocorticoids. In addition, these medications are used widely in the community and it is essential that their efficacy be assessed.

A study psychologist or psychiatric nurse practitioner will review all screened subjects, conduct a psychiatric interview at baseline and at any other time the staff requests. S/he will continue to monitor and ensure the ongoing psychiatric care of patients with their primary clinical psychiatrists and therapy teams and also provide individual consultation to subjects as needed. All patients recruited will continue to receive medical and psychiatric care from their treatment teams and all participants must have a clinical provider in place. A study psychologist or psychiatric nurse practitioner will continue to work closely with the patients' clinical care treatment teams to ensure patient safety and continued appropriateness for the study from a psychiatric perspective. In summary, the study psychologist or psychiatric nurse practitioner involvement will be to provide a comprehensive psychiatric evaluation of potential study subjects, provide ongoing psychiatric monitoring of patients during the course of the study, and, be available by page for any questions that arise from study subjects, other investigators, and the patients' clinical treatment teams and psychiatric providers. S/he will review any specific psychiatric issues regarding patients involved in the protocol with the other investigators, review data and participate in all aspects of the proposed study as a key member of the research team. S/he will attend Data Safety Monitoring Board meetings and will, together with the P.I., keep the Data Safety Monitoring updated on any issues that impact patient safety.

**Physician Availability:** A physician will be available by pager at all times during the study to answer any questions or address any concerns that a subject may have. All efforts will be made to protect the confidentiality of study subjects who will be referred to by an enrollment number only.

**Patient Confidentiality:** Confidentiality of the patients will always be of paramount importance to study investigators. All data on patients will be kept in confidential study binders and electronic files accessed by only study investigators and study staff. No study subject data will be shared with persons other than those directly involved in the study, except at the documented request of the subject.

### **VIII. Potential Benefits**

Each subject will have a complete nutritional analysis and BMD performed. These data, including relative fracture risk and total calcium intake, will be made available to the subject. In addition, a physical exam and blood testing will be performed in all subjects, and these data will also be made available to the subject.

The subject's bone mineral density may increase during the study, although if it does increase, it is not known how long it will remain higher. We hope and anticipate that the information learned from this study will allow us to better understand the pathophysiology of bone loss in anorexia nervosa and to improve the treatment of patients with bone loss associated with under-nutrition.

## **IX. Monitoring and Quality Assurance**

No study procedures will be performed prior to approval by the Mass General Brigham Human Research Committee (IRB). Furthermore, all changes to the protocol or consent form will be submitted to the Human Research Committee for approval before being implemented. No data on study subjects will be shared with persons other than those directly involved in the study, except at the documented request of the study subject. Data obtained from each subject's visit will be reviewed by the investigators weekly. Study staff will review the completeness of case report form (CRF) entries, source documents, and informed consent during and immediately following the visit.

All adverse events, collected at all study visits, will be reported to the Human Research Committee (IRB) according to Mass General Brigham adverse event Reporting Policy and to the FDA according to Title 21 of the Code of Federal Regulations. A study-related adverse event will be considered serious if it results in any of the following outcomes: death, a life-threatening adverse event, inpatient hospitalization or prolongation of existing hospitalization, or a persistent or significant incapacity or substantial disruption of the ability to conduct normal life functions. Additionally, any medical event that may jeopardize the subject and may require medical or surgical intervention to prevent one of the outcomes listed. All adverse events will be reported to the Data Safety Monitoring Board every 6 months, and this report will be submitted to the IRB every 6 months. Safety data will also be reported to [REDACTED] as follows:

Suspected Unexpected Serious Adverse Reaction (SUSARs) will be reported to [REDACTED] at the time of regulatory submission. Pregnancy/Lactation exposure and any associated reports/outcomes (i.e. unexpected pregnancy, pregnancy of partner, spontaneous abortion, congenital anomaly etc.) will be reported within 1 business day of sponsor awareness, for reports meeting serious criteria. Reporting to [REDACTED] will not exceed 15 calendar days of sponsor awareness for non-serious reports.

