If screen 25-OH vitamin D level is  $<40$  ng/ml, subjects will be given one loading dose of oral vitamin D2 (ergocalciferol) 50,000 IU at the baseline visit. All subjects will be asked to take a standard dose of 1000 mg calcium and 800 IU vitamin D supplements daily throughout the study. It is our experience from multiple clinical trials that women with anorexia nervosa are extremely compliant with calcium and vitamin D supplementation.

After the baseline visit, follow-up visits will occur at monthly intervals during the first 12 months of the study so that the romosozumab or placebo injections can be administered by a study physician, nurse practitioner, or study nurse. In rare cases where subjects are unable to travel to MGH, the study

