**Major adverse cardiac event.** In a randomized controlled trial in postmenopausal women, there was a higher rate of major adverse cardiac events (MACE), a composite endpoint of cardiovascular death, nonfatal myocardial infarction and nonfatal stroke, in patients treated with romosozumab compared to those treated with alendronate. Subjects who have had a myocardial infarction or stroke within the preceding year will be excluded from participation in the study.

**Osteonecrosis of the jaw (ONJ).** ONJ is a potentially serious condition that can present as a sore in the mouth through which the jaw bone is sometimes visible. The gum tissue over the bone may heal slowly or not heal at all. How this happens is poorly understood. The symptoms of ONJ include pain or infection in the jaw bone and gums. Subjects will be instructed that if they develop any of these symptoms, they should see their doctor who should examine her mouth to determine if she has ONJ. The risk of developing ONJ is higher in patients who have had tooth removal, gum surgery, infections in the mouth, dental implants or other dental procedures. Subjects will be instructed that it is important that they maintain good oral hygiene and avoid dental procedures immediately before and during their participation in the study, if possible. They will also be instructed that their study doctor and dentist should discuss the benefits and risks of any dental procedure. Additionally, they will be instructed to tell their dentist that they are taking romosozumab before a dental procedure is planned. Although ONJ has been reported rarely in patients receiving romosozumab, we will take all possible precautions to prevent it from occurring, specifically, we will exclude all subjects with an invasive dental procedure within 6 months prior to the baseline visit or planned dental procedure over the next 6 months, and will require all subjects to have had a dental exam within 1 year prior to enrolling in the study.

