### **Data and Safety Monitoring**

A Data Safety Monitoring Board will be established at Massachusetts General Hospital consisting of five members -- the following five are staff members at Massachusetts General Hospital -- [REDACTED]

[REDACTED]

[REDACTED]

[REDACTED]

[REDACTED]

The Data Safety Monitoring Board will meet twice a year after study activation, or more often as needed. The Board will review all study procedures, all adverse events, study violations, exceptions and deviations as well as study inclusion and exclusion criteria. The Board will review all safety monitoring blood tests and study data as available. The data reviewed by the Data Safety Monitoring Board will be

blinded as to randomization assignment, except in cases in which the Data Safety Monitoring Board or study investigators feel that unblended data should be reviewed due to safety concerns. All study related serious adverse events will be reported to the Board within 24h of occurrence. Based on recruitment, review of adverse events and other parameters to be established by the Board, the Board may request an interim analysis or request unblinding or halting of the study for safety concerns or other issues that impact on safety.

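### A serious event judged unrelated to the study, even a death, has no committed route to the Data Safety Monitoring Board faster than the six-monthly report

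*Combined protocol and SAP*

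**What the plan says.** Three statements set the Board's reporting timetable.

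- **Definition (Section IX, Monitoring and Quality Assurance).** "A study-related adverse event will be considered serious if it results in any of the following outcomes". Death, life-threatening events and inpatient hospitalization are among the outcomes listed. A further clause adds "any medical event that may jeopardize the subject and may require medical or surgical intervention to prevent one of the outcomes listed", with no condition on relatedness.
- **Expedited notice (Data and Safety Monitoring).** "All study related serious adverse events will be reported to the Board within 24h of occurrence".
- **Routine notice (Section IX).** "All adverse events will be reported to the Data Safety Monitoring Board every 6 months". On meetings, the Data and Safety Monitoring subsection says: "The Data Safety Monitoring Board will meet twice a year after study activation, or more often as needed".

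Two other places open an earlier route to the Board. In the drop criteria of Section III, a participant found medically unstable is to be assessed by the Board. Near the end of Section VII, the principal investigator and the study psychologist or psychiatric nurse practitioner are to keep the Board informed on matters of patient safety. Neither place gives a time limit. The drop criteria, other than pregnancy, stop applying once the zoledronic acid infusion has been given. The drop criterion for serious events is itself limited to study-related ones.

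**The concern.** Seriousness describes what happened to the participant. Relatedness is a separate opinion about cause, and the documents do not say who gives it or by what criteria. This plan uses that opinion to decide whether the Board hears within a day or at the next half-yearly report.

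The opinion is least reliable where it matters most. Section VII reports more major adverse cardiac events on romosozumab than on alendronate in a trial of postmenopausal women, and Section I acknowledges a possible cardiovascular signal. One cardiac event in one woman cannot show whether the drug contributed, so a judgement of unrelated is a weak reason to delay. The Board may request unblinding, an interim analysis or a halt, but it can act promptly only on events it has been told about. While it waits, other women continue monthly injections.

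**Working it through.** There is no statistical figure to reproduce. The check sets the rules side by side and adds the stated intervals.

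**Step 1. Does the ambiguity in the definition change the timing?** Take an event with a listed outcome that is judged unrelated.

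| Reading of Section IX | Classed as serious? | Meets the 24-hour rule? |
|---|---|---|
| Main sentence governs: seriousness requires relatedness | No | No |
| Unqualified added clause governs, or the main sentence is loosely drafted | Yes | No, because the 24-hour rule asks for relatedness again |

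Both readings leave the six-monthly report as the only scheduled route. The added clause concerns events that may need intervention to prevent a listed outcome. It could cover a treated heart attack, but it fits poorly with a death that has already occurred.

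**Step 2. Committed time to the Board once the site knows of the event.**
- Serious and judged related: 24 hours.
- Judged unrelated: up to 6 months, if the site learns of it just after a report has gone out.

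**Step 3. Time from occurrence.** Section IX says adverse events are collected at study visits. Section V says "follow-up visits will occur at monthly intervals during the first 12 months of the study"; after month 12 the visits are at months 18 and 24. Assume that the site learns of events only at visits:
- Months 0 to 12: 1 month to the next visit + 6 months to the report = about 7 months.
- Months 12 to 24: 6 months + 6 months = about 12 months.

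If participants report events by telephone between visits, both fall back to about 6 months.

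**Step 4. Who is exposed meanwhile?** Hospitalization and medical instability are drop criteria whatever the cause, until the infusion. A woman hospitalized with a cardiac event would therefore usually be withdrawn. Other participants still in the injection phase could receive up to about 6 monthly injections (6 months × 1 per month) before the Board's scheduled sight of the event.

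**Step 5. Do the earlier routes close the gap?**
- Medical instability: the Board assesses the patient, but with no deadline, and the criterion lapses at the month 12 infusion.
- Safety updates from the principal investigator and the psychologist or nurse practitioner: no deadline and no list of events.
- Extra Board meetings: held when needed, with nothing to trigger them.

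Each route makes earlier notice possible, and none commits to it.

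**The case against.** The strongest reply is that the definition is loosely drafted and was never meant to declare unrelated deaths non-serious. The drop criterion and the 24-hour rule both add a study-related qualifier, which would be redundant if seriousness already implied relatedness. Section IX also applies serious criteria to pregnancy reports without asking about cause. This stands, and it is why the definition is called ambiguous here. It does not help with timing, because the 24-hour rule carries its own qualifier.

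A second reply is that other oversight exists. Investigators review visit data weekly, and adverse events go to the IRB under institutional policy and to the FDA under federal regulation. That is correct, but weekly investigator review is not Board notice, and the IRB and FDA are different recipients. The eligibility criteria also lower cardiac risk by excluding recent infarction or stroke, hypertension, diabetes, current smoking and LDL above 190 mg/dL. That lowers the expected number of cardiac events, but the gap also covers deaths and hospitalizations of any kind.

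A reader might infer more than the documents support:
- **That the affected woman would keep receiving injections for months.** For the events at issue, the drop criteria would usually withdraw her, and they are in force throughout the injection phase.
- **That unrelated events are hidden from the Board.** All adverse events reach it every 6 months.
- **That they would be missing from a serious-event table.** The plan specifies no such table.
- **That faster notices would reveal an imbalance between arms.** The Board's data are blinded by default, and with 20 versus 10 women a comparison of rare events would be very imprecise.
- **That blinded investigators judge relatedness.** The plan does not name the assessor.

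**Conclusion.** The point holds as a gap in committed timing. A death, cardiac event or hospitalization judged unrelated is guaranteed to reach the Board only through the six-monthly report, against 24 hours for the same event judged related. Six months from site awareness is the worst case, since earlier contact is allowed. The figures of about 7 and 12 months from occurrence rest on the assumption that events are learned of only at visits.

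The gap follows from a rule the plan states, so staff who follow the text exactly would still produce the delay. The consequence is later Board action on behalf of the other participants. No efficacy analysis, sample size or endpoint is affected. The change should be made because the safeguard is cheap and the plan itself names a cardiovascular concern.

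**What to change.** 1. In Section IX, delete the study-related condition from the definition of seriousness, so that it depends on outcome alone. Complete the added clause so that it clearly belongs to that definition.
2. Record relatedness as a separate field for every adverse event, and state who assesses it.
3. In the Data and Safety Monitoring subsection, require that all serious adverse events, whatever their judged relationship to the study, be reported to the Board within 24 hours of the study team becoming aware. Running the clock from awareness also mends the current rule, which counts from occurrence and cannot be met for an event first learned of at a later visit.

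Leave the drop criteria in Section III unchanged; this point concerns reporting only. The cost is a few wording changes, one data field, and some additional expedited notices, for example for eating-disorder admissions, which should be manageable with 30 participants.

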### **Data and Safety Monitoring**

A Data Safety Monitoring Board will be established at Massachusetts General Hospital consisting of five members -- the following five are staff members at Massachusetts General Hospital -- [REDACTED]

[REDACTED]

[REDACTED]

[REDACTED]

[REDACTED]

The Data Safety Monitoring Board will meet twice a year after study activation, or more often as needed. The Board will review all study procedures, all adverse events, study violations, exceptions and deviations as well as study inclusion and exclusion criteria. The Board will review all safety monitoring blood tests and study data as available. The data reviewed by the Data Safety Monitoring Board will be

blinded as to randomization assignment, except in cases in which the Data Safety Monitoring Board or study investigators feel that unblended data should be reviewed due to safety concerns. All study related serious adverse events will be reported to the Board within 24h of occurrence. Based on recruitment, review of adverse events and other parameters to be established by the Board, the Board may request an interim analysis or request unblinding or halting of the study for safety concerns or other issues that impact on safety.

